7.3 Study procedures

Questionnaires

All questionnaires will be completed in a secured, electronic environment (e.g. Castor_that can be accessed at different time via the internet by electronic devices (telephone, tablet, or computer).

Participants will be asked to fill out the following questionnaires:

- Demographic characteristics, medical history and comorbidities

See "F1.1 Screeningsvragenlijst WoWstudy Versie1.1 04-04-2018"

Participants will fill out this questionnaire regarding baseline characteristics, demographics, life-style (including diet) and medical history.

- Gluten-free dietary compliance questionnaire (Biagi questionnaire)

See "F1.2_Biagi vragenlijst naleving glutenvrij dieet_WoWstudy_Versie1.1_28-03-2018"

This questionnaire of Biagi et al. (24) consists of a few questions that can be

administered in a few minutes even by non-expert personnel. The numerical result makes it possible to monitor the strictness of GFD compliance by non-expert personnel. The questionnaire provides a final score in five levels (0–4), which can

be grouped into three levels. Patients with scores of 0 or 1 are in fact those who do not follow a strict GFD. Patients with scores of 2, on the other hand, follow a GFD but with important errors that require correction. Patients with scores of 3 and 4 follow a strict GFD.

- Rome criteria for IBS and Functional Dyspepsia

See "F1.3_Rome IBS_WoWstudy_Versie1.1_28-03-2018"

Irritable Bowel Syndrome (IBS) and Functional Dyspepsia (FD) will be diagnosed according to the Rome criteria (III and IV for IBS and IV for FD). The Rome criteria will be completed at screening as part of the medical history, since there is a big overlap between IBS and NCGS symptoms.

Positive and Negative Affective Schedule (PANAS)

See "F1.4_PANAS_WoWstudy_Versie1.1_28-03-2018"

The Positive and Negative Affect Schedule (25) will be used to assess mood/emotional wellbeing (using the Dutch version; see Peeters *et al.*, 1996 (26); Engelen *et al.*, 2006 (27)) during the test day (every hour) and at the end of day 1, 2, 3.. The PANAS consists of a list of 20 emotions, including 10 positive emotions (Positive Affect (PA), *e.g.* excited, positive, happy) and 10 negative emotions (Negative Affect (NA), *e.g.* nervous, depression, sadness). Participants will be instructed to rate to what extend each emotion had been experienced during that day (as opposed to only considering their current emotional state), using a scale from 1 ('not at all') to 5 ('extremely').

- Generalized Anxiety Disorder assessment (GAD-7)

See "F1.5 GAD7 WoWstudy Versie1.1 28-03-2018"

The GAD-7 is a validated 9-item questionnaire which has been demonstrated to be an efficient tool for screening for generalized anxiety disorder and assessing its severity in clinical practice and research (29). The GAD-7 will be completed at home between the screening and the test day by means of electronic questionnaires.

- Patient Health Questionnaire-9 (PHQ-9)

See "F1.6 PHQ9 WoWstudy Versie1.1 28-03-2018"

The PHQ-9 is a validated multipurpose instrument for screening, diagnosing, monitoring and measuring the severity of depression. It incorporates DSM-IV depression diagnostic criteria with other leading major depressive symptoms into a brief self-report tool. The PHQ-9 can also be administered repeatedly, which can reflect improvement or worsening of depression in response to an intervention (28). The PHQ-9 will be completed at home between the screening and the test day by means of electronic questionnaires.

- Patient Health Questionnaire-15 (PHQ-15)

See "F1.7 PHQ15 WoWstudy Versie1.1 28-03-2018"

The PHQ-15 is a brief, self-administered questionnaire that is useful in screening for somatization and in monitoring somatic symptom severity in clinical practice and research (30). The PHQ-15 will be completed at home between the screening and the test day by means of electronic questionnaires.

- Symptom diary and Bristol Stool Scale

See "F2 Klachten Dagboek WoWstudy Versie1.0 05-03-2018"

Participants will be asked to rate their daily symptoms on 100-mm VAS scale as well as rating their stool pattern during each hour (only after bowel movement) at the test day and at the end of day 1, 2, 3. The diary includes six sections: 1. Stool frequency and consistency - Bristol Stool Scale, 2. GI Symptoms, 3. Overall GI symptoms, 4. Other symptoms, 5. What did you eat today?, 6. Medication. The questionnaire can be completed at the MUMC+ or at home (or work), provided that the same tool is used to complete all the hourly questionnaires.

Blood sampling to exclude coeliac disease

Serological tests (*i.e.* anti-tTG) to rule out coeliac disease will be carried out during screening, if tests to exclude coeliac have not been done before and if participants still consume traces or very low amounts of gluten in their current diet (according to the Biagi questionnaire). This is estimated to be in about 20% of the participants who indicate interests to participate in the study. In this subgroup of participants, a venepuncture (10mL blood sample) will be done to exclude coeliac disease by means of serological tests on anti-tTG IgA. Blood samples will be collected from an antecubital vein in the fore-arm. This his may lead to minor discomfort and can cause small and transitory hematoma/bruises to appear.

7.4 Withdrawal of individual subjects

Participants can leave the study at any time without having to provide a reason if they wish to do so without any consequences. The investigator can decide to withdraw a subject from the study for urgent medical reasons.

7.4.1 Specific criteria for withdrawal (if applicable)

The investigator can decide to withdraw a participant from the study for urgent medical reasons.

7.5 Replacement of individual subjects after withdrawal

We do not expect dropouts, because the study is not very burdensome in a physical way and so, is not very difficult to complete. When participants withdrawn from the study after signing informed consent but prior to the test day, or prove to be unsuitable on the basis of the screening and therefore cannot participate in the study, an alternative candidate may be selected, in order to ultimately meet the calculated sample size/power. If participants withdraw from the study before the test day, these results will be destroyed immediately after completion of the study.

When participants withdrawn from the study at the test day (*i.e.* after randomisation), before or after receiving and consuming the study breads because of intolerable symptoms, there will be no replacement of participants. These participants are included in the intention-to-treat analysis, because this is seen as important regarding tolerance of the intervention. In that case, missing VAS-scores for the remaining days of the study period will be imputed with the last observation carried forward.

7.6 Follow-up of subjects withdrawn from treatment

After withdrawal, no follow-up of participants will take place. In case of withdrawal due to medical complications, participants will be referred to a general physician.

7.7 Premature termination of the study

There are no expected reasons for premature termination of the study. However, if certain urgent medical problems occur during study (for example SAEs that result in death or are life threatening) the investigator (if necessary together with the medical committee) can decide to halt the study to check whether it is safe to proceed or if termination is preferred.

8. SAFETY REPORTING

8.1 Temporary halt for reasons of subject safety

In accordance to section 10, subsection 4, of the WMO, the sponsor will suspend the study if there are sufficient grounds that continuation of the study will jeopardise subject health or safety. The sponsor will notify the accredited METC without undue delay of a temporary halt including the reason for such an action. The study will be suspended pending a further positive decision by the accredited METC. The investigator will take care that all participants are kept informed.

8.2 AEs, SAEs and SUSARs

8.2.1 Adverse events (AEs)

Adverse events are defined as any undesirable experience occurring to a subject during the study, whether or not considered related to the food intervention (*i.e.* study breads). All adverse events reported spontaneously by the participants or observed by the investigator or his staff will be recorded.

8.2.2 Serious adverse events (SAEs)

A serious adverse event is any untoward medical occurrence or effect that:

- results in death;
- is life threatening (at the time of the event);
- requires hospitalisation or prolongation of existing inpatients' hospitalisation;
- results in persistent or significant disability or incapacity;
- is a congenital anomaly or birth defect; or
- any other important medical event that did not result in any of the outcomes listed above due to medical or surgical intervention but could have been based upon appropriate judgement by the investigator.

An elective hospital admission will not be considered as a serious adverse event.

The coordinating investigator will report all SAEs to the sponsor without undue delay after obtaining knowledge of the SAE by the concerning investigator. Additionally, the sponsor will report the SAEs through the web portal *ToetsingOnline* to the accredited METC that approved the protocol, within 7 days of first knowledge for SAEs that result in death or are life threatening followed by a period of maximum of 8 days to complete the initial preliminary report. All other SAEs will be reported within a period of maximum 15 days after the sponsor has first knowledge of the serious adverse events.

8.3 Follow-up of adverse events

All AEs will be followed until they have abated, or until a stable situation has been reached. Depending on the event, follow up may require additional tests or medical procedures as indicated, and/or referral to the general physician or a medical specialist. SAEs need to be reported till end of study within the Netherlands, as defined in the protocol.

9. STATISTICAL ANALYSIS

Statistical analyses will be carried out using IBM SPSS statistics 23.0 for Macintosh (Chicago IL, USA) and GraphPad Prism 6.0 for Macintosh (La Jolla, CA, USA). Baseline characteristics (including the outcomes of the questionnaires at baseline) will be analysed and summarized using descriptive statistics. Dichotomous variables will be presented as percentages and will be analysed using the Chi-square test. A Fisher exact test will be performed if necessary. Normality of continuous or ordinal variables will be evaluated by the Kolmogorov-Smirnov test and histograms for normality of the distribution. These variables will be analysed with the Wilcoxon signed-ranked test, when the distribution of the variables is non-parametric. If the variables are normally distributed a paired t-test will be performed. The independent variables will be analysed with the Mann-Whitney test if the distribution of the variables is nonparametric. If the variables are normally distributed an independent sample t-test will be done. Correlations will be assessed according to Spearman or Pearson and regression analyses will be done. An intention-to-treat analysis (ITT) will be conducted for all outcomes. All data will first be examined for accuracy of data-entry and missing values. A p-value < 0.05 is considered to be statistically significant. A similar study will be performed at the University of Leeds (United Kingdom), which will eventually provide us with the opportunity to compare the outcomes. Data will be analysed for each study site separately and also together using study site as a factor in the analysis.

9.1 Primary and secondary study parameter(s)

The main research question will be analysed by means of repeated measures univariate analyses of variance (ANOVA) with Expectancy ("gluten-containing" vs. "gluten-free") and Gluten ("gluten-containing bread" vs. "gluten-free bread") as between-subjects factors and Time (baseline and after intervention) as repeated measure factors on the several dependent measures including changes in overall (GI) symptom score, gastro- and extraintestinal symptoms, positive and negative affective parameters, and well-being. Only significant main- or interaction effects revealed by these procedures will be further examined by post-hoc univariate tests, corrected for multiple comparisons.

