Frozen packages of bread portions for the test day will be provided by European Bakery Innovation Centre, Papendrecht, The Netherlands, with a label that refers to the "expectancy" arm, but the actual treatment is blinded. Participants will be asked to report their GI symptoms, extra-intestinal symptoms, stool characteristics, and the PANAS in an electronic diary at baseline (at 8.00AM) and every hour till 4.30PM. After 4.30PM, participants will go home and will be allowed to eat freely as normal. During the study visits and telephonic contacts, the presence of serious adverse events will be checked. Participants will also be instructed to contact the researcher if their health status changes.

If participants are unable to stay at the MUMC+, Amsterdam UMC or WUR the entire day, they will receive the breakfast and the baseline questionnaire at the study location and can do the follow-up (*i.e.* completing the hourly questionnaire and consuming the study lunch) at home or at work, provided that all hourly questionnaires will be completed on the same tablet or notebook. If necessary, a study tablet will be provided for the test day. Subjects will receive a text message 5 minutes before each timepoint they have to fill in a questionnaire and will be informed that time of completion will be logged. Furthermore, participants have to adhere to the dietary restrictions. If possible, participants consume the study lunch in the presence of the researcher. Alternatively, participants are asked to provide pictures as proof of completely consuming the study lunch. The starting time of the test day can be flexible (before 9.00AM) and results in a shift of all time points, therefore it does not affect the structure of the test day. Any alterations in the test day (e.g. location of completing the hourly questionnaires) will be logged and taken into account during analyses.

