4.4 Sample size calculation

Sample size calculation is based on our primary outcome measure, the overall symptom score, using a visual analogue scale (VAS). Since no data of overall symptom score based on expectancy in an NCGS population are available, we based our sample size calculations on a well-designed study most comparable to the present study by Biesiekierski et al. (2013) (17). In that study, the effects of gluten on GI symptoms in patients with NCGS after dietary reduction of fermentable, poorly absorbed, short chain carbohydrates (17) were examined. They reported an increase in mean overall symptom score after the ingestion of either 16g gluten/day (high-gluten arm) of 10.3mm in VAS-score with a standard deviation of 12.8mm (data obtained by requesting raw data from author (17)). In the study of Biesiekierski et al. (2013) a change of 20mm in VAS of overall symptom score was considered clinically relevant. Since our study has a different study design in which expectancy may play a major role and symptom scores may increase less, we deem an overall symptom difference in VAS-score of 15mm to be clinically relevant. Using a difference in overall mean symptoms of 15mm with a standard deviation of 12.8mm, power of 80% and two-sided alpha of 0.05, a sample size of 20 participants per group are required. So, a total sample size of 80 participants is required.

In addition, in order to account for potential drop outs due to drop-out after randomisation and during the test day for a reason other than intolerable symptoms, we ask permission to include max 5% (*i.e.* 4) extra participants, resulting in maximal 84 participants in total. Power analysis was conducted in the statistical power analysis program "G*power, version 3.1 for Macintosh" (19).

Version number: 3.0, date 16-12-2020

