5.3 Escape medication (if applicable)

We do not expect that the use of escape medication will be necessary. However, participants are permitted to use paracetamol if necessary. The use of nonsteroidal anti-inflammatory drugs (NSAIDs) and opioids are not allowed during the test day. The number of tablets, dose, and the reason for the medication use have to be reported in the electronic diary. If paracetamol does not work adequately and participants experience intolerable symptoms during the study, the involved gastroenterologists in this study ([name]) will advise on whether or not to stop the intervention. In that case, VAS-scores for the remaining questionnaires were replenished using the highest VAS-score achieved thus far.

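### The repeated-measures ANOVA in section 9.1 drops participants with an unfilled missing score, so the intention-to-treat analysis promised for all outcomes is not delivered for losses unrelated to intolerable symptoms or for non-VAS outcomes

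*Protocol*

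**What the plan says.** Section 9 sets the population: "An intention-to-treat analysis (ITT) will be conducted for all outcomes".

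Section 9.1 sets the method: "The main research question will be analysed by means of repeated measures univariate analyses of variance (ANOVA". Expectancy and Gluten are the between-subjects factors, and the repeated factor is "Time (baseline and after intervention) as repeated measure factors". The same procedure serves the overall GI score, the individual intestinal and extra-intestinal symptoms, positive and negative affect, and well-being.

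Missing scores are dealt with in two other places, both limited to intolerable symptoms and to VAS scores:

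- Section 7.5, for test-day withdrawals because of intolerable symptoms: "These participants are included in the intention-to-treat analysis, because this is seen as important regarding tolerance of the intervention". For them, "missing VAS-scores for the remaining days of the study period will be imputed with the last observation carried forward".
- Section 5.3, for stopping the intervention because of intolerable symptoms: "VAS-scores for the remaining questionnaires were replenished using the highest VAS-score achieved thus far".

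For other losses, section 4.4 asks for up to 4 extra participants (5% of 80, at most 84 in total) "in order to account for potential drop outs due to drop-out after randomisation and during the test day for a reason other than intolerable symptoms". Section 7.2 extends the randomisation list to 90 so that new participants can take new numbers after dropouts. Section 7.6 ends follow-up at withdrawal.

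Section 3.2 lets participants who cannot stay on site do the rest of the test day elsewhere, "completing the hourly questionnaire and consuming the study lunch) at home or at work".

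**The concern.** The protocol fixes both the population and the method, and the two do not fit together. Intention-to-treat requires every randomised participant to be analysed in the assigned arm. Classical repeated-measures ANOVA works on complete rows, so a participant missing one Time level leaves the analysis altogether, including the scores that were recorded.

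The fill-in rules repair this for one group (intolerable symptoms) and one type of data (VAS). The result is a mixture: imputed scores for the worst reactors and deletion for everyone else. Adding participants restores the count but does not bring back those who were randomised and lost.

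At stake is the comparability of the randomised arms. Participants know which expectancy arm they were told, and so does the investigator (7.2). Expectancy is also the primary contrast (section 2, E+G- versus E-G-). If staying to the end or completing forms depended on that message, the completers would differ between E+ and E-. The protocol gives no data showing that this happens, so it is a possibility that deletion leaves open, not a demonstrated bias.

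**Working it through.** **1. Who has a score at every Time level?**

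| Situation | Rule in the protocol | In the 9.1 ANOVA? |
|---|---|---|
| Intolerable symptoms, VAS outcome | 5.3 (highest so far) or 7.5 (last observation) | Yes, with imputed scores |
| Intolerable symptoms, PANAS or stool outcome | None | No, if the 'after' value is missing |
| Lost after randomisation for another reason, any outcome | None; extra participants (4.4, 7.2) | No, if the 'after' value is missing |
| One hourly form missed, others present | None | Depends on how the 'after' score is formed |

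Rows two and three contradict intention-to-treat for all outcomes. Row four is open: if 'after intervention' is a mean or maximum over the hours, one missed form removes nobody.

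**2. The two fill-in rules differ.** Section 5.3 carries the highest VAS so far into the remaining questionnaires. Section 7.5 carries the last VAS into the remaining days. A participant who stops and withdraws for intolerable symptoms can fall under both, and the rules agree only if the last recorded score is also the highest.

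**3. The planned sample size, as reference.** Inputs from 4.4: difference 15 mm, SD 12.8 mm, 80% power, two-sided alpha 0.05, 20 per group.

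- n per group = 2 × (1.960 + 0.842)² × (12.8/15)² ≈ 11.4, so 12 by normal approximation. The exact t-test needs 13 (power 81.8%).
- The stated 20 is therefore not reproduced. At 20 per group the exact t-test power is 95.1%. This is a separate matter; here 95.1% serves only as the starting value.

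**4. Loss under the model as written.** The missing rate p per score is an assumption (1%, 2%, 5%), taken as independent across scores. The share kept is (1 − p) if only the 'after' score can be missing and (1 − p)² if either score can be. Power is for a two-sided two-sample t-test at 15 mm and SD 12.8 mm, with 20 × share kept per arm.

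| p | 'After' score only: kept of 80 | Power | Either score: kept of 80 | Power |
|---|---|---|---|---|
| 1% | 79.2 | 94.9% | 78.4 | 94.7% |
| 2% | 78.4 | 94.7% | 76.8 | 94.2% |
| 5% | 76.0 | 94.0% | 72.2 | 92.8% |

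**5. The 4 dropouts allowed for in 4.4.** If they were lost and not offset, power at 15 mm is 94.0% with one lost per arm (19 v 19), and 92.4% if all four came from one arm of the primary contrast (16 v 20).

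**6. A model that 9.1 does not state.** If the eight post-bread hourly forms were each a Time level, the share kept would be (1 − p)⁸ = 0.923, 0.851 or 0.663, a loss of 8%, 15% or 34%. Power at 15 mm would be 93.3%, 91.2% or 82.6%.

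**The case against.** The strongest reply has four parts.

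- **The informative losses are kept.** Withdrawals for intolerable symptoms stay in the analysis with imputed VAS scores. This stands for the primary VAS outcome. A reader might infer from the choice of ANOVA that the whole primary analysis is one of completers; 5.3 and 7.5 do not support that.
- **Missed hourly forms need not matter.** Section 9.1 names two Time levels, and how the hourly scores form the 'after' value may be set in an analysis plan not shown. This also stands. A reader might infer losses of 8% to 34% and a serious fall in power, but that requires eight hourly Time levels, which 9.1 does not state. Even then, power at the planning difference of 15 mm stays above the 80% target.
- **Arm-dependent missingness is conjecture.** Section 3.2 provides a text reminder before each form, logged completion times and a study tablet if needed. Section 5.2 makes the supervised site the usual setting. The baseline form precedes the expectancy message, so baseline loss cannot depend on it. These safeguards reduce the risk. They do not cover a participant who leaves during the test day.
- **Missing-data detail belongs in the analysis plan, and 4.4 does not say that lost participants are excluded.** True in general. But the protocol itself states the ANOVA, the intention-to-treat promise, the two partial rules and the extra participants. Taken together they leave lost participants with no score and so outside the analysis. That is a conflict in the text, not a silence.

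**Conclusion.** The point holds in a limited form. For participants lost after randomisation for reasons other than intolerable symptoms, and for PANAS and stool outcomes in anyone with missing data, the stated method analyses completers while section 9 promises intention-to-treat. For the primary VAS score, participants with intolerable symptoms are retained, but under two rules that can give different values.

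The numerical effect is small: about 1% to 5% of participants per missing 'after' score, and power for 15 mm of about 93% to 95% against 95.1% with complete data. These figures assume 1% to 5% missingness per score, independence across scores, the two Time levels in 9.1, and the SD of 12.8 mm from 4.4. Power is not the issue. What needs correcting is the definition of the analysis population and the possible selection that deletion leaves in the expectancy comparison. The direction and size of any such selection cannot be judged from the protocol.

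**What to change.** In section 9.1, replace the repeated-measures ANOVA with a linear mixed model on all recorded hourly scores from the 8-hour test day. Include baseline, Expectancy, Gluten, hour and their interactions, and state the primary contrast as E+G- versus E-G- over the 8 hours. Use the same approach for hourly PANAS scores, and say how missing stool data are handled.

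Also:

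- Define the intention-to-treat set as everyone randomised and told an expectancy arm. State that those with at least one post-message score contribute to the model, and report by arm the number with none.
- State in 4.4 and 7.2 that participants lost after randomisation are analysed with the data they have and are not replaced in the analysis, even if extra participants are recruited.
- Reconcile the fill-in rules in 5.3 and 7.5 so that one rule applies to each situation, and say how filled-in scores enter the model.

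The cost is a change of analysis text, with no new data and no added burden for participants. Mixed models are available in the software named in section 9. A covariance structure has to be chosen in advance. The within-8-hours contrast must also be made explicit, which sharpens the present comparison of baseline with 'after intervention' and so is more than rewording. The model uses partial records but cannot recover anyone with only a baseline score, so those participants still need to be counted and reported.

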7.2 Randomisation, blinding and treatment allocation

After screening and subsequent inclusion in the study, each participant will be assigned to a unique participant identifier code. Participants will be randomly assigned to one of the following experimental conditions:

- 1. Gluten-free expectation and actually receiving gluten-free oat bread (E-, G-).
- 2. Gluten-free expectation but actually receiving gluten-containing oat bread (E-, G+).
- 3. Gluten-containing expectation but actually receiving gluten-free oat bread (E+, G-).
- 4. Gluten-containing expectation and actually receiving gluten-containing oat bread (E+, G+).

The randomisation lists will be generated by an independent co-worker from the same department as the principal investigator who is not further involved in the study, using a publicly available procedure through the internet (http://randomizer.org). This random number generator performs balanced permutations, resulting in an equal number of participants per treatment order followed. Participants will be randomly allocated to the treatment conditions and there will be a stratification on gender using block randomisation (block sizes of 8). The randomisation scheme will be up to n=90, this to be sure in case of dropouts, to randomize potential (new) participants to a new randomization number.

The investigator has no access to the randomisation list that conceals the intervention code. However, since expectation may play a role in the experience of symptoms, the investigator is unblinded to the expectation arm since the investigator has to inform the participant about allocation to the gluten-free or gluten-containing expectation group. Of course, the investigator is blinded to the actual treatment. The randomisation list will be kept in a sealed envelope by the head of the department (prof. dr. [name]), to reveal the treatment in case of medical emergency. Primary investigators of all participating centres will receive the contact details of prof. dr. [name]. The condition numbers as allocated by the independent colleague, who will carry out the randomisation, are registered by the investigator in the screening and enrolment log. Furthermore, the same co-worker will keep the randomisation lists. The "randomization key" will be provided to the investigator only after all experimental and statistical procedures have been completed.

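### The primary ANOVA treats baseline as a level of Time on 'changes' and names no primary term: the raw-score Expectancy main effect is halved, and baseline and gender are not adjusted for

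*Protocol*

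**What the plan says.** Protocol section 9.1 sets the primary analysis as a repeated-measures ANOVA. Expectancy and Gluten are the between-subjects factors, and the within-subject part is given as "Time (baseline and after intervention) as repeated measure factors on the several dependent measures including changes in overall (GI) symptom score". Any significant main or interaction effect then leads to post-hoc tests; the section does not say which effect answers the primary question. Section 2 ties the primary objective to one comparison, E+G- against E-G-.

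On randomisation, section 7.2 states that "there will be a stratification on gender using block randomisation (block sizes of 8"). Gender appears in no analysis section. Study site does, in section 9: "Data will be analysed for each study site separately and also together using study site as a factor in the analysis".

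Section 3.2 has participants complete the baseline symptom questionnaire at 8.00AM, before they are told their expectancy group.

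**The concern.** Three things are at issue.

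- **Outcome and factor do not match.** If the dependent variable is change, its baseline level is zero for everyone and Time carries no information there. If it is the raw score, calling it a change is wrong. The two readings give different Expectancy rows in the ANOVA table.
- **No term is named.** On raw scores the Expectancy main effect averages a pre-allocation baseline, where the true difference is zero, with the post score. Anyone who takes that row as the expectancy effect reports half of it, with low power.
- **Precision is left unused.** Baseline is subtracted, although it is collected before allocation is disclosed and is a valid covariate. The stratification factor is left out.

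**Working it through.** **Inputs from the protocol (section 4.4).** The effect and spread are set by "Using a difference in overall mean symptoms of 15mm with a standard deviation of 12.8mm". The calculation aims at 80% power with a two-sided 5% test and arrives at 20 per group. The SD comes from an outside study that reported an increase "of 10.3mm in VAS-score with a standard deviation of 12.8mm", so I read 12.8 mm as the SD of change; the protocol does not say so outright.

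**Assumptions.** Neither the baseline-post correlation rho nor the SD ratio k = baseline SD / post SD is in the protocol. I use rho = 0.3, 0.5 and 0.7, and k = 1, 0.7 and 0.5.

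**The plan's own figure.** A two-sample t test with 15 mm, SD 12.8 mm, 80% power and two-sided 0.05 needs 13 per group (exact noncentral t), not 20. At 20 per group the power is 95.1%. That mismatch is a separate matter; the 95.1% is the reference used below.

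**Step 1: the terms on raw scores.** Let delta be the expectancy effect on the post score and s the post SD.
- Expectancy main effect: estimates (0 + delta)/2 = delta/2, so 15 mm becomes 7.5 mm. Its per-person variance is s²(1 + k² + 2 rho k)/4, which is s²(1 + rho)/2 at k = 1.
- Expectancy x Time: estimates delta, with per-person variance s²(1 + k² - 2 rho k). This is the change-score test.
- ANCOVA: estimates delta, with per-person variance s²(1 - rho²).

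**Step 2: power with k = 1 and SD of change 12.8 mm.**

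| Setting | Test | rho 0.3 | rho 0.5 | rho 0.7 |
|---|---|---|---|---|
| 15 mm, 20 vs 20 | raw main effect | 75.5% | 55.0% | 32.9% |
| | Expectancy x Time | 95.1% | 95.1% | 95.1% |
| | ANCOVA | 99.4% | 98.6% | 97.5% |
| 10.3 mm, 20 vs 20 | change score | 70% | 70% | 70% |
| | ANCOVA | 87% | 82% | 77% |
| 10.3 mm in both breads, 40 vs 40 | raw main effect | 74% | 54% | 32% |
| | Expectancy x Time | 94% | 94% | 94% |

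The 20 vs 20 rows correspond to E+G- vs E-G-. The 40 vs 40 rows pool over bread type, as the full-model terms do.

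**Step 3: the change-score reading.** With baseline set to zero for everyone, the main effect is the mean of 0 and the change. Estimate and standard error are both halved, so the test is unchanged. Simulation (4,000 runs, 7 mm, 40 per arm, SD 12.8 mm at each time point) gave identical rejection rates for this main effect and the change-score test: 53.6%, 68.7% and 87.8% at rho 0.3, 0.5 and 0.7. ANCOVA gave 71.0%, 80.5% and 91.3%.

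**Step 4: variance gain of ANCOVA over change scores.** Gain = 1 - (1 - rho²)/(1 + k² - 2 rho k). For example, at k = 0.7 and rho = 0.3: 1 - 0.91/1.07 = 15%.

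| k | rho 0.3 | rho 0.5 | rho 0.7 |
|---|---|---|---|
| 1 | 35% | 25% | 15% |
| 0.7 | 15% | 5% | 0% |
| 0.5 | 4% | 0% | 7% |

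The denominator minus the numerator is (k - rho)², so the gain is never negative and is zero where k = rho. At k = 0.5, power at 10.3 mm and 20 vs 20 moves only from 70% to 72%, 70% and 73%.

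**Step 5: gender.** If gender explains a share R² of the variance, adjustment multiplies the standard error by sqrt(1 - R²): 0.990 at an assumed 2% and 0.949 at 10%, a cut of about 1% to 5%. The estimate itself does not shrink when gender is left out.

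**The case against.** A reader might infer that the plan's primary test is diluted and the trial underpowered. The document does not support that. Section 9.1 acts on main or interaction effects alike, so Expectancy x Time, which is undiluted, opens the way to the post-hoc tests even when the main effect fails. On the change-score reading nothing is lost in the test either. In a randomised trial the change-score analysis is unbiased and holds its type I error.

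A reader might also infer that omitting gender dilutes the effect. It does not. If gender is prognostic, leaving it out makes inference slightly conservative, and a covariate list could in any case stand in an SAP that is not shown.

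The efficiency gain can be overstated too. The figures of 35%, 25% and 15% require equal baseline and post SDs. Section 4.2 admits only people with an overall VAS of 30 mm or less on the diet, and the baseline is taken fasted, so a smaller baseline SD is plausible. The 10.3 mm is a within-arm increase from another study, not the planned between-group difference.

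All of this stands and limits the size of the point. It does not remove the mismatch between outcome and Time factor, the unnamed term, or the unused baseline.

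**Conclusion.** The point holds in a limited form. The primary model as worded is not coherent, and it leaves open which row of the table answers the primary question. One available row, the raw-score Expectancy main effect, estimates half the true effect; for 15 mm at 20 vs 20 its power is 75.5% to 32.9% over rho 0.3 to 0.7, with k = 1 and 12.8 mm as the SD of change. The other, Expectancy x Time, is sound at about 95%.

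Adjusting for baseline instead of subtracting it never loses asymptotically. It gains between 0% and 35% of the variance over the assumed range of rho and k. With power already about 95% at the planned effect, that gain matters mainly if the true effect is smaller than 15 mm. Adding gender is worth perhaps 1% to 5% of the standard error, under an assumed R² of 2% to 10%.

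**What to change.** Replace the baseline/after ANOVA for the primary outcome by ANCOVA. The dependent variable is the post-intervention overall VAS. The model contains Expectancy, Gluten and their interaction, with the 8.00AM baseline VAS, gender and study site as covariates; site is already a factor under section 9. Name E+G- vs E-G- from this model as the primary contrast. Because ratings are hourly, state which post-intervention score or summary is meant.

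If the repeated-measures ANOVA is kept, use raw scores, delete the reference to changes as its outcome, and name Expectancy x Time, not the Expectancy main effect, as the test.

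The variables are already collected, so this is a change to the analysis text. It costs one degree of freedom each for baseline and gender and two for the three sites, against 80 - 4 = 76 residual degrees of freedom with 80 participants in four cells.
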